7.1.3 TREATMENT AND FOLLOW UP OF AEs

AEs will be followed up until they have returned to baseline status or stabilized. Details of follow up will be recorded in the study record including if return to baseline status or stabilization cannot be achieved.

In the event of medically significant unexplained abnormal laboratory test values, the tests will be repeated and followed up until they have returned to the normal range or the baseline value and/or an adequate explanation of the abnormality is found. All details will be included in the study record.

If the study drug is discontinued due to an AE or a laboratory abnormality, the study medication will not be reinstated. If the investigator decides to discontinue study drug treatment, the rationale for their decision will be provided in the AE comment/SAE narrative field of the study record.

Study drug will be discontinued in the presence of an SAE that is deemed to be related or possibly related. Thromboembolic events or any event which a participant finds intolerable, which cannot be mitigated with therapy, will be cause for VOR discontinuation. Participants experiencing a $\geq 50\%$ increase in seizure frequency, as compared to baseline at any time during the treatment period will be discontinued from study medication. Additionally, participants presenting with status epilepticus at any time during the treatment period will be discontinued from study medication.

7.1.3.1 Project Specific Adverse Events

The following AEs are noted in the VOR product monograph as warning and precautions, based on CTCL clinical trials in adults.

Thromboembolism

Pulmonary embolism and DVT have been reported as drug-related AEs in clinical trials with VOR. In greater than 1000 patients with hematologic malignancies and solid tumors who have been treated with VOR as monotherapy, or in combination with other chemotherapy agents, in completed and ongoing clinical studies, the proportion of patients that experienced a venous thromboembolic event was approximately 5.0%⁴⁰. An increase in the incidence of venous thromboembolic events was also found in patients with advanced non-small cell lung cancer who received VOR (400 mg once daily) in combination with chemotherapy (carboplatin and paclitaxel) as compared to patients who received chemotherapy alone. In this study, deep venous thrombosis and/or pulmonary embolism was reported in 6.5% (8/124) of patients in the VOR chemotherapy treatment arm compared to 2.4% (3/124) of patients in the placebo/chemotherapy treatment arm⁴⁰.

Investigators will closely monitor patients for signs and symptoms of these events, particularly in patients with a prior history of thromboembolic events. In the instance of a thromboembolic event, study drug will be discontinued.

Hyperglycemia

Hyperglycemia has been observed in patients receiving VOR⁴⁰. Serum glucose will be monitored as part of the biochemistry laboratory safety panel as summarized in [Table 5: Schedule of events](#).

. In the event of hyperglycemia, adjustment of diet or anti-hyperglycemic therapy may be trialed in the event of intolerable hyperglycemia.

Gastrointestinal Disturbances

Gastrointestinal disturbances, including nausea, vomiting and diarrhea have been reported very commonly in patients treated with VOR⁴⁰. Antiemetic and/or antidiarrheal medications may be trialed in the event of moderate to severe nausea, vomiting, diarrhea. Additional potassium and magnesium monitoring should be considered in symptomatic patients.

Dehydration

Dehydration has been reported as a common serious drug-related adverse experience in clinical trials⁴⁰. Participants will be instructed to consume enough fluids to maintain adequate daily hydration, as adjusted for age.

Hematologic Disturbances

Treatment with VOR is associated with dose-related hematologic adverse effects⁴⁰. Participants will be monitored as per laboratory testing schedule to identify such disturbances. Additionally participants will be advised to contact the investigator if presenting with frequent bruising, nose bleeds or gum bleeding, blood in urine or stools, or petechiae.

QT/QTc Prolongation

Treatment with VOR is associated with QT/QTc interval prolongation⁴⁰, which is suspected to increase the risk of Torsade de pointes. Torsade de pointes may be asymptomatic or may be experienced as dizziness, palpitations, syncope, or increased seizures. Participants will be instructed to contact the investigator if presenting with these symptoms. Additional ECG monitoring may be conducted.

7.2 HANDLING OF SAFETY PARAMETERS

7.2.1 REPORTING OF SERIOUS ADVERSE EVENTS

All new AEs occurring during the study should be recorded in the study record. AEs that occur intermittently will be recorded as a single AE. AEs will be collected and reported for up to 6 weeks after the last dose of study medication.

7.2.2 EXEMPTION OF PROJECT SPECIFIC SERIOUS AEs FROM IMMEDIATE REPORTING TO HEALTH AUTHORITIES AND IRBs

For any clinical AE or abnormal laboratory test value that is serious [as defined in Section 7.1.1.3], the investigator will complete SAE reporting in the study record within 24 hours of the study team becoming aware of the event. The REB and Health Canada will be notified as per reporting requirements.

SAEs monitoring and reporting will commence at the time following administration of the first dose of study medication until 6 weeks following administration of the last dose of study medication. At any time after the 6-week period following the last dose of study drug, only SAEs considered by the investigator to be related to study drug or protocol procedures will continue to be reported as stipulated.

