3.1.2 PHASES OF STUDY

There are three phases to the study.

Phase 1: Screening period

During this phase, participants will be screened for study eligibility, which will last a total of 4 weeks. This will include several baseline investigations including full review of medical history and current medications, seizure frequency, physical examination, vital signs, laboratory safety testing, pregnancy testing for eligible patients, and electrocardiogram (ECG) (see Section 5 Schedule of Assessments and Procedures for complete list of screening procedures). In addition, baseline seizure frequency will be determined during this period. Clinically stable participants, fulfilling all eligibility criteria (see sections 4.2 and 4.3) will be enrolled in the treatment period of the study.

Phase 2: Treatment period

The duration of the treatment period will be 6 weeks. VOR will be given as fixed doses of 230 mg/m²/day. Following the enrollment visit, participants will visit the clinic for 2 more visits every 2 weeks, plus an end of treatment (EOT) visit (see Section 5.1 for detailed schedule). Participants may be seen more frequently for unscheduled visits for follow up of AEs, etc. as per the investigator's discretion. Study visits will include a physical examination, height and weight measurement, vital signs, pregnancy testing (required patients only). Safety monitoring during the treatment period will include laboratory safety testing and ECG. Investigators will review current medications, AEs, seizure diary/frequency at each visit. Investigators will assess study medication adherence at all visits; unused study medication will be returned to site at each visit and new study medication will be dispensed by local pharmacy, as recommended by the investigator. Unused study medication will be destroyed as per local standard operating procedures. All assessments and visit procedures will occur as stipulated in Section 5: Schedule of Assessments and Procedures.

Phase 3: Follow-up period

A safety follow-visit (SFU) will take place 6 weeks after the EOT Visit. The SFU visit will include a physical examination, height and weight measurement, vital signs. Safety monitoring for this visit will include laboratory safety testing and ECG. Investigators will review AEs since last visit and seizure diary/frequency. Any ongoing AEs will be followed by the investigator until resolution or stability.

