3.3 NUMBER OF SUBJECTS

12 pediatric patients meeting the criteria of medically intractable epilepsy in addition to the other eligibility criteria, recruited from the ACH Neurology Outpatient Clinic will be enrolled in study.

SECTION 4: STUDY POPULATION

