- ECG: An ECG will be collected through a service contract via the Cardiology department at the ACH. Participants who have had a clinically indicated ECG, found to be non-clinically significant, within 1 month prior to screening will not require another ECG, provided the investigator deems the participant stable. The ECG may be collected at any point following the screening visit until enrollment visit (Visit 2), as long as results are available and may be reviewed by the investigator prior to enrollment

5.1.2 ENROLLMENT VISIT – VISIT 2

Participants meeting all inclusion and no exclusion criteria will be enrolled. Participants will receive study medication at this visit.

The following study specific activities will be completed at the enrolment visit (Visit 2):

- Medical history: Medical history and Epilepsy history will be reviewed once again to ensure that any new history since screening is captured.
- Anthropometrics: height and weight will be captured to establish baseline growth and to calculate body surface area (BSA) for proper medication dosing
- Vital signs: blood pressure and heart rate
- Pregnancy test: a urine pregnancy test will be done for all applicable participants
- Study medication dispensed: Study medication will be prepared and dispensed by the ACH research pharmacy, with dosage based on participant BSA ([see Section 6.1](#)). Participants will be counseled by the investigator on: how to take the medication, including to consume enough fluids to maintain adequate daily hydration, as adjusted for age; to contact the investigator promptly if excessive vomiting/diarrhea; or dizziness, palpitations, syncope, or increased seizures develop; or to contact the investigator immediately or present to the emergency room if leg swelling, chest pain, or shortness of breath develop. Participants will take VOR, 230 mg/m² once daily, preferably at the same time of the day throughout the treatment portion of the study, in addition to their prescribed evidence-based medical care for seizure management.

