6.2.3 DOSE INTERRUPTIONS

If a dose is missed, it should be taken as soon as possible. If the participant does not remember until it is nearly time for the next dose, the participant should skip the missed dose and go back to the regular schedule. A double dose of should not be taken.

There will be no temporary interruptions of study medication due to safety reasons. If study medication is stopped due to safety reason, there will be no re-challenge.

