8.2.2 ANALYSIS

8.2.2.1. SAFETY & TOLERABILITY ANALYSIS

Safety and tolerability will be assessed by calculating the incidence rate of AEs per number of drug days from the time medication is started through to the completion of the SFU (or 42 days following the last dose of study medication). This will be done for the following time points: 14 days following drug initiation; 30 days following drug initiation; 42 days following drug initiation; and 42 days following drug discontinuation. AEs will be further stratified by mild/moderate AEs, severe AEs, and SAEs, as well as project specific AEs (thromboembolism, hyperglycemia, gastrointestinal disturbances, dehydration, hematologic disturbances, QT/QTc prolongation).

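### An intermittent AE is recorded once but divided by all drug-days since drug start, so the rate for an AE type already under way is pulled down over time and persistent symptoms look like single early episodes

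*Combined protocol and SAP*

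**What the plan says.** On recording, Section 7.2.1 states: "AEs that occur intermittently will be recorded as a single AE". The heading refers to serious events, but the sentence follows an instruction about all new AEs, so it covers non-serious events too. The protocol does not define intermittent.

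On analysis, Section 8.2.2.1 states: "Safety and tolerability will be assessed by calculating the incidence rate of AEs per number of drug days from the time medication is started". The time points are "14 days following drug initiation; 30 days following drug initiation; 42 days following drug initiation; and 42 days following drug discontinuation". Results are then split by severity, by seriousness and by project-specific class, one of which is gastrointestinal disturbances. Nothing in that section ends a child's time at risk at first onset, counts episodes, or counts an AE again if it is still recurring at a later time point.

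On exposure, Section 3.1.2 gives a six-week treatment period ("The duration of the treatment period will be 6 weeks"), Section 5.1.2 specifies once-daily dosing, and Section 6.2.3 adds: "There will be no temporary interruptions of study medication due to safety reasons". Drug-days therefore continue to accrue after an AE starts, unless the child stops for good.

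Section 5.3.1 collects a date of onset and a date of resolution for each event, together with intensity, relationship, outcome and treatment. It does not ask for a count of episodes.

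**The concern.** The numerator behaves like a count of first onsets, while the denominator is all exposure, including days on which a child with an open intermittent record cannot add another event of that type. Presented as a series over 14, 30 and 42 days, such a rate drifts downward for reasons unrelated to the symptom.

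Two things are at stake. First, a reader may take a decline as a sign that AEs come early and settle. Section 1.1.4.1 describes most related valproate AEs that way, and Sections 1.1.4 and 1.1.4.3 use valproate as the context for inferring vorinostat's tolerability. Second, a child who vomits every few days from week 1 to week 6 and a child who vomits once on day 3 contribute identically to the planned rates. Gastrointestinal events, which Section 7.1.3.1 expects to be very common, are a natural place for this to happen. With 12 children and no control arm, no comparator would expose the drift.

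**Working it through.** The plan states no AE rate, so there is no figure of its own to reproduce. The check is direct arithmetic.

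**Inputs.** One record per intermittent AE (7.2.1); drug-days from drug start, at days 14, 30 and 42 (8.2.2.1); 42 days of once-daily treatment (3.1.2, 5.1.2); 12 children (3.3); anticipated overall AE incidence of up to 55% (5.2.1); adult monograph incidences of diarrhea 46.5%, fatigue 45.3%, nausea 38.4% and vomiting 11.6% (1.1.3).

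**Step 1: one child, onset by day 14, symptom recurring unchanged.** Rate(T) = 1/T.
- Day 14: 1/14 = 71 per 1000 drug-days
- Day 30: 1/30 = 33 per 1000
- Day 42: 1/42 = 24 per 1000

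The fall is 1 − 14/42 = 67%. At 80% compliance the values are 89, 42 and 30 per 1000, the same relative fall. With onset on day 20 they are 0, 33 and 24, so the pull begins only after onset. If the time points are read as separate intervals, the pattern is 1/14, 0/16, 0/12, which is steeper.

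**Step 2: the same symptom with each episode counted.** An episode every 2 days gives 7/14, 15/30 and 21/42, a constant 500 per 1000. The fall in Step 1 therefore comes from the counting rule and not from the symptom.

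**Step 3: the total over 12 children.** Suppose 7 children each have one such AE by day 14 (an assumption; 55% of 12 is 6.6).
- No further AEs: 7/168, 7/360, 7/504 = 41.7, 19.4, 13.9 per 1000.
- Flat total: needs 15 records by day 30 and 21 by day 42 (15/360 = 21/504 = 41.7 per 1000).
- Ten new distinct AEs per 14 days after day 14: 41.7, 51.2, 53.6 per 1000, a rise.

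The effect is a downward pull on AEs already recorded. It does not force the total down.

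**Step 4: expected size for one AE type.** Assume a constant daily hazard λ of first onset and one record per child. The expected planned rate is (1 − e^(−λT))/T, whereas the true onset rate is λ throughout.
- An incidence of 55% over 42 days gives λ = −ln(0.45)/42 = 0.019, or about 0.02.
- With λ = 0.02: day 14, (1 − e^(−0.28))/14 = 17.4 per 1000; day 42, (1 − e^(−0.84))/42 = 13.5 per 1000; ratio 0.78.

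For an incidence p assumed to accrue over 42 days, the day-42 to day-14 ratio is p / {3 × [1 − (1 − p)^(1/3)]}:

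| AE (adult monograph) | p | Ratio |
|---|---|---|
| Diarrhea | 0.465 | 0.82 |
| Fatigue | 0.453 | 0.83 |
| Nausea | 0.384 | 0.86 |
| Vomiting | 0.116 | 0.96 |

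**Step 5: the at-risk denominator.** If drug-days stop at first onset, expected time at risk per child is (1 − e^(−λT))/λ. Dividing expected onsets, 1 − e^(−λT), by this returns λ at every T, which is 20 per 1000 for λ = 0.02. The drift disappears.

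The fourth time point, 42 days after discontinuation, is separate. Read literally, drug-days stay at 42 and the rate is unchanged or rises with new AEs. If follow-up days were counted, the single contribution would be 1/84 = 12 per 1000.

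**The case against.** The strongest reply is that an incidence rate measures new onsets, that persistence is a different quantity, and that recording a recurrent AE once is not wrong in itself. That stands. The difficulty lies only in pairing that count with exposure that keeps growing after onset.

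A reader might infer that the primary safety result must decline by construction. The documents do not support this. Section 8.2.2.1 pools AEs by severity and broad class; the gastrointestinal class alone combines nausea, vomiting and diarrhea, so one child can add several records, and Step 3 shows that the total can stay flat or rise.

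A reader might also take 67% as the expected fall. It is the contribution of one child chosen for early onset. Hazards of 0.05 or 0.10 per day would give ratios of 0.58 or 0.44, but they imply that about 88% or 98% of children are affected by day 42, against the anticipated maximum of 55% for all AEs together. At the monograph incidences the fall is 4% to 18%, which in 12 children is well within chance variation.

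Nor does the text say that a returning AE is never counted again. Intermittent is undefined, new AEs are to be recorded, and Section 5.3.1 includes events that worsen, so a resolved AE that returns or worsens might open a new record.

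Finally, no objective or decision rule rests on a time trend. The benchmarks in Section 5.2.1 are percentages, and discontinuation for intolerable AEs is unaffected. These points limit the consequence. They do not repair the mismatch in the one rate that 8.2.2.1 defines.

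**Conclusion.** The concern holds in a limited form. For an AE type that has already started and is recorded once, the planned rate is pulled down as drug-days accrue, and it cannot separate a persistent symptom from a single early episode. The total AE rate need not fall.

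The expected size is modest: a day-42 to day-14 ratio of about 0.78 at an incidence near 55%, and about 0.82 to 0.96 at the adult monograph incidences. These ratios rest on three assumptions: a constant hazard of first onset, accrual of the quoted incidences over 42 days, and one record per child per AE type. The 55% figure is for all AEs together, so it is a high calibration for any single type.

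This is an inexpensive improvement to the AE part of the primary endpoint. It does not invalidate the safety analysis.

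**What to change.** In Section 8.2.2.1, calculate the rate for each AE type and each project-specific class on drug-days at risk: from drug start to first onset, or to the last drug-day if there is none. Beside it, report the number of children with that AE present in days 1–14, 15–30 and 31–42, using the onset and resolution dates already collected under Section 5.3.1.

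In Section 7.2.1, state that the dates on a single intermittent-AE record run from its first to its last episode; otherwise the interval table cannot be built reliably. Such a record may still span an interval without an episode. If episodes are to be dated individually, that needs one extra CRF line per episode, which is optional.

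The cost is SAP wording and one extra table, with no new visits, participants or data items for the core change. It should be settled before analysis.

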7.2.3. PREGNANCY

Pregnancies occurring in female participants exposed to the study medication, or partners of male participants exposed to the study medication, will be reported to the REB. Female participants, or partners of male participants will be instructed to notify the investigator as soon as possible. Female participants will be instructed to discontinue taking the study medication immediately. Study medication will be permanently discontinued in female participants and an EOT and SFU visit will be conducted as per protocol. Participants or partners of male participants will be followed until the conclusion of pregnancy. Pregnancies occurring up to 90 days after the completion of the study medication will be followed in the same manner.

The investigator will counsel and discuss with the participant/partner of participant the risks of continuing with the pregnancy and the possible effects of early exposure to study medication on the fetus.

Where a SAE occurs in the pregnant female participant, the SAE must be collected separately, regardless of whether it is pregnancy related or not.

SECTION 8: STATISTICAL CONSIDERATION AND ANALYTICAL PLAN

8.1 PRIMARY AND SECONDARY STUDY ENDPOINTS

8.1.1 PRIMARY ENDPOINTS

The primary endpoint for this study will be the incidence of related AEs and SAEs, and discontinuation of therapy due to intolerable AEs.

8.1.2 SECONDARY ENDPOINT

The secondary endpoint for this study will be efficacy. Treatment response will be evaluated by:

- Proportion of patients who have at least a 50% reduction in seizures
- Change in seizure remission status

8.2 STATISTICAL AND ANALYTICAL METHODS

8.2.1 SAMPLE SIZE

The rationale for selection of sample size to investigate safety in a pilot study in this population was based on feasibility in regards to recruitment potential, according to prior knowledge of our referred/existing clinical base, and cost of conducting this study. Further, as this medication has not been tested in this population and rate of AEs in this population is not known, a power based/effect size calculation of sample size cannot be determined.

8.2.2 ANALYSIS

8.2.2.1. SAFETY & TOLERABILITY ANALYSIS

Safety and tolerability will be assessed by calculating the incidence rate of AEs per number of drug days from the time medication is started through to the completion of the SFU (or 42 days following the last dose of study medication). This will be done for the following time points: 14 days following drug initiation; 30 days following drug initiation; 42 days following drug initiation; and 42 days following drug discontinuation. AEs will be further stratified by mild/moderate AEs, severe AEs, and SAEs, as well as project specific AEs (thromboembolism, hyperglycemia, gastrointestinal disturbances, dehydration, hematologic disturbances, QT/QTc prolongation).

